11.2.1.2 Quantitative MRI criteria

Quantitative density evaluations will be carried out in the "ROIs" (Regions of interest) of the area of the nucleus pulposus of the affected segment and of the 3-5 healthy neighboring segments in the T2 images taken before the start of treatment and 6 and 12 months after inclusion. The quotient of the value obtained in the affected segment divided by the mean of the healthy segments will be used as a measure of the relative water content, with 1.00 being the normal value. The same ROIs should be used for the measurements obtained at 3 times, before treatment and 6 and 12 months after. The procedure is illustrated in Figure 4 (taken from (Orozco et al., 2011)). The increase

in the quotient approaching the value of 1 is will consider a sign of rehydration. The descriptive analysis of the values of this variable It will be expressed by the mean, standard deviation, 95% confidence interval of the mean.

To find out if there are differences between baseline and at 6 and 12 months, the no test will be used. parametric for paired Wilcoxon data.

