3.3. Primary Criteria

3.3.1. Radiographic criteria

□ In profile radiography, carried out with the same technical characteristics and hourly (before noon), the height of the space will be measured intervertebral in millimeters, this being the variable that will be compared with measurements that occurred over time (6 and 12 months after implantation of MSV). An increase in height will be understood as rehydration disc associated with an increase in proteoglycans and cellularity of the NP.

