5.5 CRITERIA FOR NON-RESPONSE TO TREATMENT

It will be considered that there is no response to treatment if 12 months after the intervention there is no significant clinical changes observed in the questionnaires and / or changes in MRI images showing signs of improvement in dehydration. Shall be deemed the partial response in case of evidence of clinical or regenerative improvement in isolated.

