11. STATISTICAL ANALYSIS

11.1 SAMPLE SIZE

As it is a phase I-II study, in which the safety of the product under study is evaluated, the sample was fixed at 12 patients per branch (24 patients in total)

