11.2 STATISTICAL METHOD USED

In all descriptive analyzes, categorical variables will be summarized using frequencies and category percentages. For the distributions of continuous variables, will present the mean and its Standard Deviation, the median and the 25th and 75th percentiles of the distribution, the number of cases, minimum and maximum value.

All hypothesis tests will be two-tailed, with a significance level of 5%. The The result of a hypothesis test will comprise the 95% Confidence Interval of the variable (s) analyzed. To calculate the statistical significance of the differences between the two groups, a normality analysis of the distribution will be carried out and compare the means using the double-tailed t-test or the Wilcoxon, depending on whether the population is Gaussian or not.

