11.3.7 Efficacy

Changes in pain, disability and quality of life indices will be described in the baseline situation and at 3, 6 and 12 months of treatment, which will be compared as specified in 11.2.

The frequency and percentage of patients presenting signs of regeneration at 12 months of the different interventions, comparing the values as specified in 11.2.

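### The MRI rule for rehydration sets no minimum change, so a regeneration percentage built on it cannot be read within one arm and is a weaker comparison than the continuous quotient

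*Combined protocol and SAP*

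**What the plan says.** Section 11.2.1.2 divides the T2 reading of the affected segment by the mean of 3-5 healthy neighbouring segments, with 1.00 as normal, before treatment and at 6 and 12 months. An increase "in the quotient approaching the value of 1 is will consider a sign of rehydration". No minimum change, repeatability figure or error allowance is given. Disc height is treated the same way. Section 3.3.1 states "An increase in height will be understood as rehydration", and both 3.3.1 and 11.2.1.1 tie a rise to more proteoglycans and cells in the nucleus.

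Section 11.3.7 adds a patient-level result, "The frequency and percentage of patients presenting signs of regeneration at 12 months", to be compared across interventions by the methods of 11.2. The label is not defined there. Section 11.2 tells the analyst to "compare the means using the double-tailed t-test or the Wilcoxon, depending on whether the population is Gaussian or not"; it names no test for proportions. Section 5.5 refers to "changes in MRI images showing signs of improvement in dehydration", again without a threshold, and counts isolated clinical or regenerative improvement as a partial response.

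The quotient is also kept continuous. Section 11.2.1.2 gives its mean, SD and 95% confidence interval and a paired Wilcoxon test of baseline against 6 and 12 months. Section 11.3.4 has a general comparison of means at 0, 6 and 12 months. Section 11.1 fixes 12 patients per arm without an effect size, SD or power.

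**The concern.** Any repeated measurement moves a little. If a rise of any size counts as improvement, random error alone puts many unchanged discs in the improved group. Regeneration is part of the working hypothesis in Section 3, so a rate near one half in the MSV arm could be presented as support for it when nothing had changed. The same label could make a patient a partial responder under 5.5 without clinical benefit.

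The second issue is efficiency. Reducing a continuous measurement to yes or no loses information, and there are only 24 patients. The one regeneration comparison that 11.3.7 names is this percentage.

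**Working it through.** The plan gives no power or false-label figure to reproduce. From the documents: 12 per arm (11.1), two-sided 5% level (11.2), t-test or Wilcoxon (11.2). Assumed, because the documents give no values: normal change scores with equal SD, no dropout, an unchanged control arm unless stated, and effects of 0.5 to 2.0 SD of change.

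**Step 1: false labels under an any-rise rule.** P(rise) = Phi(drift / SD of change).

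- No drift: Phi(0) = 50%, or 6 of 12 expected per arm (95% range 3 to 9). P(at least 6 of 12) = (1 + 924/4096)/2 = 0.613.
- Drift of -0.5, -0.25, +0.25 and +0.5 SD: 31%, 40%, 60% and 69%.
- Inclusion criterion 1 (5.1.1) allows one or two discs, and no rule combines them. If two discs are assessed and a rise in either counts, the no-drift rate is 67% (correlation 0.5) to 75% (independent).

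**Step 2: power at 12 per arm.** The continuous comparison of change uses the noncentral t distribution with 22 degrees of freedom and noncentrality d x sqrt(12/2); at d = 1.2 this is 1.2 x 2.449 = 2.94. The percentage comparison uses rates Phi(d) against Phi(0) = 50%, with every pair of binomial outcomes enumerated.

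| Effect (SD of change) | Rates compared | Continuous t-test | Percentages, Fisher | Percentages, t-test on 0/1 |
|---|---|---|---|---|
| 0.5 | 69% v 50% | 22% | 9% | 18% |
| 1.0 | 84% v 50% | 65% | 28% | 45% |
| 1.2 | 88% v 50% | 80% | 38% | 56% |
| 1.5 | 93% v 50% | 94% | 53% | 70% |
| 2.0 | 98% v 50% | 99.7% | 70% | 84% |

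The uncorrected chi-square test gives the same power as the t-test on 0/1 data. A Wilcoxon rank-sum test on the continuous change has about 77% power at 1.2 SD (simulation).

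Relative loss from 1.0 to 2.0 SD:

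- Fisher: 1 - 0.284/0.649 = 56%, down to 1 - 0.699/0.997 = 30%.
- t-test on 0/1: 1 - 0.448/0.649 = 31%, down to 1 - 0.844/0.997 = 15%.

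If controls drift down by 0.5 SD and the difference is 1.2 SD, percentage power is 49% (Fisher) or 67% (t-test on 0/1), so the loss is smaller but remains. At a 50% rate in both arms the type I error is 2.3% with Fisher and 6.4% with the other two tests.

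**Step 3: what a cut-off would do.** Counting only rises above 1.96 SD of change, with all spread in change treated as error, lowers false labels to 1 - Phi(1.96) = 2.5%. At 1.2 SD the rates become Phi(1.2 - 1.96) = 22% against 2.5%, and power falls to 8% (Fisher) or 21% (t-test on 0/1). A cut-off cures the labelling but not the loss of power.

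**The case against.** The strongest reply has four parts.

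First, the continuous analysis is already planned: 11.2.1.2 and 11.3.4 keep it, and 11.2 supplies a general two-group test. This stands in part. The percentage is an addition, so the trial as a whole does not lose the power shown above. But the test in 11.2.1.2 is within patients, 11.3.4 does not name a between-arm contrast of change, and the regeneration comparison that 11.3.7 sends to 11.2 is the percentage.

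Second, no passage says that one positive quotient change makes a patient regenerated. Section 11.2.1.2 speaks of rehydration and 11.3.7 of regeneration, and the former may only give the direction in which to read a continuous variable. This stands: the link is inferred. The any-rise rules are, however, the only imaging rules in the readable plan, and an undefined label would itself need a definition.

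Third, there is a control arm. A reader might infer that the rule would produce a false claim for MSV. Noise labels both arms alike, 3.2 calls for comparison with control, and 11.5 says the improvement seen with placebo must be discounted. The risk is confined to reading one arm's rate alone.

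Fourth, Sections 3.3.2 and 11.2.1.2 refer to Figure 4 for the MRI procedure. The figure and its legend were not available in the text reviewed, so the absence of an error allowance is established only for the readable text.

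**Conclusion.** The point holds in a limited form. If the percentage in 11.3.7 rests on the any-rise rule, about half of unchanged discs would be labelled improved in either arm, assuming symmetric error and no drift; the range is 31% to 69% for drifts of half an SD either way. A single arm's rate is therefore not evidence of regeneration. As a between-arm test, the percentage has 38% to 56% power where the continuous change has 80%, at an assumed 1.2 SD effect that the documents neither give nor exclude.

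A reader might go further and say that the percentage analysis throws away most of the power. The figures do not support that. With the t-test that 11.2 names, the relative loss is 15% to 31% for effects of 1 to 2 SD. It passes one half only with Fisher's exact test, which the plan does not name, and only for effects up to about 1.2 SD. The change is still worth making, because the better analysis uses data the trial already collects.

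**What to change.** - In 11.3.7, make the regenerative-efficacy analysis the between-arm difference in the continuous 12-month quotient, adjusted for the baseline quotient, with its 95% confidence interval. The Wilcoxon test on change can serve as a check. State how two affected discs in one patient are combined.
- Define the regeneration label, and keep any percentage descriptive and shown for both arms.
- If a repeatability cut-off is used, for example 1.96 x SD of change, state that it lowers false labels to about 2.5% but leaves only about 8% to 21% power at 1.2 SD, so it is not for testing. The SD could come from the healthy discs already read, each divided by the mean of the others: 24 x 3 = 72 to 24 x 5 = 120 discs.
- Report disc-height change as a between-arm difference, without inferring proteoglycans or cellularity.

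The cost is SAP wording and a small calculation on existing readings, with no new scans or patients. Fewer patients would be labelled improved under a cut-off. The healthy-disc SD assumes that those discs are stable and have error similar to degenerated ones, which the documents do not show; ratios within a patient also share denominators, so they are not independent. Baseline adjustment uses one degree of freedom; the power figures above are for unadjusted change.

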11.3 POPULATION AND ANALYSIS

Assessment definitions that are created to define the populations of the analyzes in this studio.

11.3.1 Evaluable patients

A patient will be considered evaluable provided that he has undergone the specified interventions (Control or allogeneic MSV).

11.3.2 Efficacy population (Per protocol (PP) population):

Secondary efficacy endpoint analysis will be based on all patients who do not have incurred in major protocol violations, and have at least one rating final efficacy of the graft.

11.3.3 Safety population:

It is the population that includes all evaluable patients who have undergone one of the three study treatments. The security population will be the population of analysis of the safety variables of the treatment.

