3.1. Main goal

□ To evaluate the viability and safety of allogeneic MSV, applied by percutaneous injection in the nucleus pulposus area for the treatment of lumbar degenerative disc disease, verifying that each of the the procedures established in the protocol and recording the possible adverse effects related to cell therapy and those that may arise for the duration of the clinical trial, whether or not related to the same.

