4.2 Overall study design

The study consists of 2 arms, one experimental with allogeneic MSV, and another control in the to be injected into the area of the paravertebral muscles near the injury saline serum containing 1% mepivacaine (1 ml of 2% mepivacaine + 1 ml of saline) in identical volume and subject to the same maneuvers as the intervention on the arm experimental. Participants in the study will be offered the possibility of, once completed the study, receive MSV treatment if it proves beneficial and the patient so wishes. The inclusion criteria in both arms are identical, but after recruiting patients will be randomly assigned to one of the treatments. The Cell manufacturing will be carried out by Citospin at the facilities of the Park Scientist of the UVa and the application and monitoring will be carried out at the Clinical Hospital University of Valladolid. 24 patients diagnosed with low back pain and / or low back pain attributable to disc degeneration and evidence of proven continuity of the external fibrous ring in the magnetic resonance image. The patients will be evaluated clinically, by the previous imaging studies (X-ray and MRI). If they are considered inclusive, they will be provided with the information regarding the clinical trial and the "Patient Information Sheet" (Annex II), citing them for the Inclusion visit. In the "Inclusion Visit", if the patient decides to participate in the trial, they must sign the "Informed Consent Document" and a visit will be scheduled for the practice of MRI and radiographs, which will be considered the pattern on which the possible determinable changes in the controls at 6 and 12 months. If you are MRI and X-rays have been recently performed and their characteristics are valid for the study, its repetition can be avoided. In this visit, basic analytics will also be requested, serology for HIV, lues and hepatitis B and C, and a serum sample will be obtained that will be sent to the Cell Production Unit for filing in the Seroteca. Although the Positive serology is not a criterion for exclusion of the recipient in the present test, it will be performed for epidemiological and preventive purposes. At the next visit (V0), it will be verified that all the inclusion criteria persist and that no exclusion is presented and the patient will be randomized (blind for him) in one of the two treatment groups and the date of implantation of MSV (V1). Once the mobile application is made, the patients will be followed up safety and to determine efficacy as established in the visit program (V2 to V5, see later).

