5.1 INCLUSION AND EXCLUSION CRITERIA

5.1.1. Inclusion criteria

1. Lumbar degenerative disc disease of one or two discs with predominance of pain lumbar and / or persistent sciatica after conservative treatment (medical and physiotherapy) of more than 6 months of evolution.

2. Complete fibrous ring, capable of containing the cellular implant, demonstrated with in the MR image (Adams stages 2, 3 and 4) (Adams et al., 2000).

3. Decrease in the height of the disc space of more than 20% measured

radiographically in lateral image.

4. Absence of spinal infection.

5. Hematological and biochemical analyzes without significant alterations that contraindicate intervention

6. The patient is able to understand the nature of the study.

7. Written informed consent of the patient.

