11.2.1 Main objectives, main variables

- Evaluate the feasibility and safety of the use of allogeneic MSV injected into the disc space for the treatment of lumbar degenerative disc disease and pain and the disability it causes.

The variables that will be used to evaluate safety will be the AAG number related to study medication and the percentage of patients who presented a related AGS. -Evaluate the analgesic-anti-inflammatory efficacy determined by the variation of the Low back pain assessment questionnaire scores (VAS), disability (Oswestry) and health and quality of life (SF12) at 3, 6 and 12 months.

- Evaluate regenerative efficacy using quantitative MRI imaging criteria determined by the appearance of improvements in disc dehydration at 6 and 12 months.

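### The only analysis set assigned to efficacy is per protocol, its assignment is ambiguous, no set covers all randomised patients, and feasibility has no variable or denominator

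*Combined protocol and SAP*

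**What the plan says.** **Analysis sets.** Section 11.3 defines three.
- Evaluable (11.3.1): "A patient will be considered evaluable provided that he has undergone the specified interventions".
- Efficacy, per protocol (11.3.2): "Secondary efficacy endpoint analysis will be based on all patients who do not have incurred in major protocol violations", with at least one final efficacy rating as a further condition. I found no definition of a major violation.
- Safety (11.3.3): evaluable patients who were treated.

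**Efficacy comparison.** Comparing efficacy between the arms is an objective in sections 1 and 3.2. Section 11.2 plans two-sided 5% tests: "To calculate the statistical significance of the differences between the two groups", a normality check leads to a t-test or Wilcoxon test. Section 11.3.7 opens "Changes in pain, disability and quality of life indices will be described in the baseline situation" and refers back to 11.2. Neither it nor 11.3.4 names a set.

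**Randomisation and replacement.** At V0, before the injection at V1, "the patient will be randomized (blind for him) in one of the two treatment groups" (4.2). Section 5.6 replaces an included patient who cannot be treated by another in the same group, until 12 are treated per arm, and asks for no further follow-up of the first patient. Section 6.2.1 gives the replacement the same number with an R prefix.

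**Feasibility.** It is a main objective in sections 1 and 11.2.1, and appears as viability in 3.1, which speaks of "verifying that each of the the procedures established in the protocol". Under that objective 11.2.1 gives a measure for safety: "The variables that will be used to evaluate safety will be the AAG number related to study medication", with the percentage of patients affected. It then lists the efficacy measures and gives none for feasibility.

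**The concern.** A randomised comparison is protected from selection only while patients are kept in the analysis whatever happens after allocation. A set that removes major violators and patients without a final rating gives up part of that protection, and with no second set nobody can see whether the removals mattered. The risk is not fanciful here. The doctor who applies the cells is unblinded (sections 1 and 4.1), and what counts as a major violation is left open. Replacement within the same arm adds a smaller departure, because the newcomer's arm is fixed rather than drawn afresh.

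For feasibility the stake is simpler. The plan promises an answer on a main objective but does not say what is counted or over whom, so an application that fails after assignment need not appear in any planned result.

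**Working it through.** **1. Which set applies to efficacy?**

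| Section | What it implies |
|---|---|
| 11.3.2 | Per protocol, for secondary efficacy endpoints |
| 7.1.2 | No secondary efficacy variables exist |
| 7.1.1, 11.2.1 | VAS, ODI, SF-12 and quantitative MRI are main |
| 3.4 | VAS, ODI and SF-12 are secondary criteria |
| 11.3.4, 11.3.7 | No set named |

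If secondary is read loosely, as in 3.4, efficacy is per protocol only. If it is read literally against 7.1.1 and 7.1.2, the main efficacy variables have no set. Evaluable and safety patients are all treated patients, so no set on either reading contains every randomised patient.

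**2. How large could per-protocol bias be?** The plan gives no exclusion rate, effect size or SD, so there is no figure of its own to reproduce. Inputs from the plan: 12 per arm (11.1), two-sided 5% (11.2). Assumptions: normal outcome, no true effect, and the *k* patients lowest on a score that correlates *ρ* with outcome are dropped from one arm.

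Bias in SD units = *ρ* × (sum of the absolute expected values of the *k* lowest of 12 normal values) / (12 − *k*). The three lowest expected values are −1.629, −1.116 and −0.793.
- *k* = 2: (1.629 + 1.116)/10 = 0.274 at *ρ* = 1
- *k* = 3: (1.629 + 1.116 + 0.793)/9 = 0.393 at *ρ* = 1

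Multiplying by *ρ*, and taking the t-test error from 200,000 simulated trials:

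| *ρ* | Bias, *k*=2 | Error, *k*=2 | Bias, *k*=3 | Error, *k*=3 |
|---|---|---|---|---|
| 0 | 0 | 5.0% | 0 | 5.0% |
| 0.3 | 0.08 | 5.5% | 0.12 | 5.7% |
| 0.5 | 0.14 | 6.4% | 0.20 | 7.4% |
| 1.0 | 0.27 | 11.4% | 0.39 | 16.6% |

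If both arms drop patients by the same rule, bias is 0 and the error at *ρ* = 0.3 to 0.5 is 5.3% to 5.7%.

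Standard error of the difference, in SD units:
- 12 v 12: √(1/12 + 1/12) = 0.41
- 10 v 12: √(1/10 + 1/12) = 0.43
- 9 v 12: √(1/9 + 1/12) = 0.44

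At *ρ* = 0.3 to 0.5 the bias is therefore between 0.08/0.43 = 0.19 and 0.20/0.44 = 0.45 of a standard error.

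**3. Feasibility with the assigned patients as denominator.** The number replaced in the MSV arm is an assumption. Intervals are exact (Clopper-Pearson).

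| Replaced | Treated / assigned | 95% CI |
|---|---|---|
| 0 | 12/12 = 100% | 74–100% |
| 1 | 12/13 = 92% | 64–99.8% |
| 2 | 12/14 = 86% | 57–98% |
| 3 | 12/15 = 80% | 52–96% |

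With treated patients alone as denominator, every row would read 12/12.

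**The case against.** The strongest reply is that the plan may already intend the right set. Section 11.3.2 is limited to secondary endpoints, the efficacy variables are called main, and 5.6 makes 12 evaluable patients per arm the aim of the study. The main efficacy analysis could then be on evaluable patients. That reading is available, but no sentence states it. It turns a plain per-protocol plan into an ambiguous one and leaves the need for a stated set.

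It is also fair that this is a 24-patient phase I-II trial with preliminary efficacy, and that a treated set is usual for safety. Tracking is partly in place: 5.6 requires withdrawal reasons in the CRD and mentions the exit of a replaced patient and its causes, and the R prefix marks replacements. What is missing is an instruction to report them.

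Three stronger readings are tempting, and the documents do not support them.
- *Efficacy results will be biased towards MSV.* Nothing in the plan gives the number, arm or direction of exclusions.
- *Feasibility is 12/12 by construction.* No text limits the denominator to treated patients. Section 3.1 does describe feasibility loosely, as verification of procedures.
- *Control patients count as evaluable without treatment.* The wording of 5.6 differs from 11.3.1, but its next sentence applies replacement to both arms alike. This is a wording mismatch only.

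Continued visits for treated patients with deviations are likewise a clarification. Section 5.8 already expects follow-up to continue after a single administration, although it is written about patients with adverse events.

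**Conclusion.** The point holds in a limited form. The only set assigned to efficacy is per protocol, the label on that assignment conflicts with the plan's own list of variables, and no set covers all randomised patients although a between-arm comparison is an objective. Feasibility is a main objective without a variable or denominator.

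The statistical harm is conditional and probably modest: none if exclusions are unrelated to outcome or alike in both arms, and 0.08 to 0.20 SD under the one-arm assumptions at *ρ* = 0.3 to 0.5. The 11% to 17% error rates need exclusions determined wholly by outcome in one arm, which is a worst case. The feasibility gap does not depend on those assumptions, but its numerical effect depends on how many patients are replaced. It should be corrected because the correction is cheap and the per-protocol set alone cannot show whether its exclusions mattered.

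**What to change.** (a) **11.3.2.** For every efficacy variable in 7.1.1 and 11.2.1, make the main analysis all patients who received the assigned injection (the evaluable set of 11.3.1), in the assigned arm, regardless of protocol violations. Use all ratings available at each visit and report missing ratings by arm and visit. Keep per protocol as a sensitivity analysis. State openly that this is a treated set and not full intention to treat, since outcomes of untreated patients are not collected.

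(b) **5.6 and 11.3.** Report randomised-but-untreated patients by arm with reasons, and flag R-numbered patients as not freshly randomised. An analysis without them is optional and does not restore randomisation.

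(c) **11.2.1.** Report feasibility as patients given the planned MSV injection divided by all patients assigned to MSV, including those later replaced, with an exact 95% CI. Because eligibility allows "Lumbar degenerative disc disease of one or two discs", say that the numerator requires every disc planned for treatment to have been injected.

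(d) **Wording only.** Align the two definitions of evaluable, and state that treated patients with deviations keep their scheduled outcome visits.

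I would not add an analysis that sets missing change to zero. Section 11.5 expects improvement of up to 30% from placebo. If both arms truly improve by 0.5 to 1.0 SD and 2 or 3 of 12 ratings are missing at random in one arm, zero-filling itself creates a bias of 2/12 × 0.5 = 0.08 to 3/12 × 1.0 = 0.25 SD.

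Cost: a few sentences and slightly more reporting, with no new visits. The feasibility figure may look less favourable.
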